C.1.a. Primary endpoint measurement: All vwMRIs are on a 3T scanner with a 20- or 32-channel head coil and gadolinium. The field of view is from the aorta to the top of the skull. Sequences include the following for Siemens scanners and equivalents for Phillips and GE:

Sequence	3D ToF	DWI	3D FLAIR	3D MPRAGE	PD SPACE DANTE	3D SWI	T1 SPACE DANTE	T2 SPACE DANTE
Contrast (gadolinium)	Pre	Pre	Pre	Pre	Pre	Pre	Pre/Post	Post

DANTE = Delay Alternating with Nutation for Tailored Excitation (for blood suppression); DWI = Diffusion Weighted Imaging (Tensor technique); GRE = Gradient Recalled Echo; MPRAGE = Magnetization Prepared Rapid Acquisition Gradient recalled Echo; PD = proton density; SPACE = Sampling Perfection with Application optimized Contrasts using different flip angle Evolution; SWI = susceptibility weighted imaging (with quantitative susceptibility mapping); ToF = Time-of-Flight

At the completion of patient enrollment, two neuroradiologists will examine all vwMRIs in three separate viewing sessions to prevent viewer fatigue. They will be given a rater sheet directing them to record findings in the brain and all major vessels of the cerebrovasculature, including:

- a) Stenosis: will be identified by the luminal imaging component of the vwMRI protocol (MR angiography of the head and neck). Stenosis will documented on the NIH Stroke CDE "Vessel Imaging Angiography"²⁵ for all cerebrovasculature vessels from the aorta to distal intracranial vessels. Any vessel with >25% stenosis qualifies for computation of this composite outcome.
- b) Percent atheroma volume (PAV): We will use MRI-PlaqueView (VPDiagnostics, Seattle, WA) to measure PAV in the aortic arch, cervical carotid, cervical vertebral and all major intracranial arteries. MRI-PlaqueView is a powerful application that allows identification of (a) vessel lumen and outer wall (OW), (b) atheroma (both calcified and lipid rich). PAV is measured on the cross-sectional slice with the highest % stenosis. PAV = Σ(OWarea Lumenarea)/ΣOWarea × 1

C.2. Secondary endpoint 1

Secondary endpoint 1 is post-contrast plaque enhancement for intracranial arteries and intraplaque hemorrhage for the cartotid artery, which are determined by two experienced neuroradiologist raters. If there is disagreement, then a third rater serves as a tie-breaker. The signal intensity characteristics of both endpoints have been standardized in prior literature.

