
C.2.a. Secondary endpoint 1 measurement:

a) ICAD post-contrast plaque enhancement (PPE): is a dichotomous variable evaluated on the T1 pre- and post-gadolinium sequences, with multiplanar reconstruction so the ICAD can be seen in cross section.²⁶ PPE is defined by placing a region-of-interest over areas of gadolinium enhancement in ICAD to evaluate if it is equal to or exceeds the signal intensity of the pituitary infundibulum, as previously described.²⁷

- b) Carotid intraplaque hemorrhage (IPH): MPRAGE positive plaque is defined as voxels with at least 2-fold signal intensity compared to sternocleidomastoid muscle as previously described. MPRAGE positive plaques can be reliably identified. Kappa values for inter- and intra-rater reliability for detection of MPRAGE positive plaque were 0.806 and 0.818 respectively (very good agreement).^{28,29}
- c) MRA Flow Dynamics (**MFD**): We will measure MFD using accepted quantitative MRA methodology. The VERiTAS study provided prospective confirmation of the importance of MFD as a biomarker of stroke risk for patients with ICAD. Given that MFD can easily be measured in our vwMRI protocol, we will acquire the data required for its quantification.

C.3. Secondary endpoint 2

To better understand the mechanism of Repatha's effect on intra- and extracranial atherosclerosis, we will measure the endpoint of change in cholesterol markers [LDL-C, HDL-C, lipoprotein (a), apolipoprotein B, and triglyceride level]. The change in cholesterol markers will be correlated with the primary and secondary study endpoints on vwMRI. Cholesterol values will be measured at the baseline and comparison MRIs, which are 78 weeks apart. If standard of care lab values are available within 30 days of the study visit, they can be used in place of the study lab value. An additional exploratory outcome that we will measure is the composite endpoint of "recurrent stroke," which encompasses new patient-reported symptomatic ischemic stroke, transient ischemic attack, or asymptomatic strokes that emerge between MRIs.

C.3.a. Secondary endpoint 2 measurement:

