We will fit a mixed effects linear regression model, specifically a LOESS smoothing curve, to change in stenosis/PAV and on-treatment LDL-C, HDL-C, and lipoprotein(a). We will also use a multivariable linear regression model with the outcome of the primary endpoints, adjusted for covariates that could be confounders such as age, gender, smoking, statin use/dose and relevant medical comorbidities. The primary endpoints will also be compared to an assumed value of 0% change in stenosis and PAV that would correspond to optimal medical management without a PCSK9 inhibitor. Although, some studies have suggested statin therapy can reduce carotid atherosclerosis, no such effect is known for ICAD. For this analysis, we will use linear mixed effects model to detect differences in the stenosis and PAV endpoints between patients taking Repatha or the presumed historical control values of 0% change. For the secondary endpoints, we will use logistic and linear regression depending on the nature of the variable and use the primary predictors of on-treatment LDL-C, HDL-C, and lipoprotein(a). For the exploratory endpoint of recurrent stroke, we will use the above mentioned methods as well as a Cox proportional hazards model for the endpoint of recurrent stroke with the observed rate in this study compared to controls matched according to degree to stenosis of the index artery. Due to differences in arterial structure and flow dynamics, there may be a more significant plaque reduction in certain intracranial vessels. We anticipate subgroup analyses, for example comparing change in stenosis or PAV in the middle cerebral artery versus the vertebral artery.

D.2. Power Analysis

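### The secondary endpoints have only association analyses on lipids: nothing stated estimates whether plaque enhancement, intraplaque hemorrhage, MRA flow dynamics or lipids changed from baseline to week 78

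*Combined protocol and SAP*

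**What the plan says.** Section C.2 defines the first secondary endpoint: "Secondary endpoint 1 is post-contrast plaque enhancement for intracranial arteries and intraplaque hemorrhage for the cartotid artery". Section C.2.a says that enhancement "is a dichotomous variable evaluated on the T1 pre- and post-gadolinium sequences", and it also lists MRA flow dynamics (MFD), to be measured by a quantitative method. None of the three is worded as a change from baseline.

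Section C.3 defines the second: "we will measure the endpoint of change in cholesterol markers", covering LDL-C, HDL-C, lipoprotein(a), apolipoprotein B and triglycerides. On timing it says: "Cholesterol values will be measured at the baseline and comparison MRIs, which are 78 weeks apart". On use it says: "The change in cholesterol markers will be correlated with the primary and secondary study endpoints on vwMRI".

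Section D.1 gives the secondary endpoints one sentence. It says "For the secondary endpoints, we will use logistic and linear regression depending on the nature of the variable" and that the models will "use the primary predictors of on-treatment LDL-C, HDL-C, and lipoprotein(a"). The comparison with an assumed 0% change, also in D.1, is stated for stenosis and PAV only. Section B.1 describes a single-arm study of 150 patients, and the schedule in B.9 has vessel wall MRI and lipid measurement at the start and at Day 546.

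**The concern.** With no control arm, a treatment signal can appear only as within-patient change or as a difference from an external value. The slope of enhancement or hemorrhage on achieved LDL-C answers another question: whether patients with lower LDL-C at week 78 differ from those with higher LDL-C. Enhancement could fall in most patients with that slope at zero, or stay constant overall with the slope well away from zero.

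Section A.5 presents the study as the basis for designing a later randomized trial. Estimates of how far these markers move are what that design would need, and the stated analyses do not produce them.

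There is a second, conditional problem. Lipids are measured twice, so the on-treatment value is the week-78 value and change is week 78 minus baseline. If the D.1 sentence applies to secondary endpoint 2, the predictor is part of the outcome.

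**Working it through.** The documents give no sample size, power or effect size for any secondary endpoint, so there is no stated figure to reproduce.

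**Step 1: which analysis covers which endpoint.**

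| Endpoint | Stated analysis | Estimate of change from baseline? |
|---|---|---|
| Stenosis, PAV (primary) | Lipid models, adjusted regression, comparison with 0% change (D.1) | Yes |
| Enhancement, hemorrhage, MFD | Regression on on-treatment lipids (D.1); correlation with lipid change (C.3) | No |
| Change in five lipids | Correlation with imaging endpoints (C.3); D.1 regression if the sentence applies | No |

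D.1 also does not say whether the outcome for enhancement or hemorrhage is baseline status, week-78 status or change.

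**Step 2: what this means for a dichotomous endpoint (illustration).** From the documents: 150 patients and 25-30% loss (D.3), so at the upper loss rate 150 × 0.70 = 105 completers; two-sided 0.05 (D.2). Assumed, because the documents give no rates: one lesion per patient, enhancement falling from 60% to 40%, latent baseline/follow-up correlation 0.6, and no relation to lipids. In 2,000 simulated trials, logistic regression of week-78 enhancement on three lipid predictors rejected for LDL-C in 4.45% of runs, which is its false-positive rate. An exact McNemar test on the same data rejected in 94%. With enhancement constant at 60%, the rates were 5.35% and 3.25%.

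**Step 3: the built-in correlation, if D.1 covers lipid change.** Let B be baseline, F follow-up, k = SD(F)/SD(B) and r = corr(B, F). Then

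corr(F - B, F) = (k - r) / sqrt(k² + 1 - 2rk).

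For k = 1 this reduces to sqrt((1 - r)/2). The documents give neither k nor r, so both are assumed:

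| k | r = 0 | r = 0.3 | r = 0.5 | r = 0.7 | r = 0.8 |
|---|---|---|---|---|---|
| 0.75 | 0.60 | 0.43 | 0.28 | 0.07 | -0.08 |
| 1.00 | 0.71 | 0.59 | 0.50 | 0.39 | 0.32 |
| 1.25 | 0.78 | 0.71 | 0.66 | 0.61 | 0.60 |

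Worked cell: k = 0.75, r = 0.5 gives 0.25 / sqrt(0.5625 + 1 - 0.75) = 0.25 / 0.901 = 0.28.

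By Fisher's z at n = 105, the chance of p < 0.05 for k = 1 is 1.00, 1.00, 1.00, 0.985 and 0.91 across the row. For k = 0.75 it is 1.00, 0.996, 0.82, 0.11 and 0.13. The mean change appears nowhere in the formula.

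**Step 4: check by simulation.** Assumed SD 30 at both visits and r = 0.5, n = 105, 2,000 runs, change regressed on on-treatment LDL-C alone. With true mean change 0, the slope was significant in 100% of runs and a paired t-test in 5.0%. With true mean change -50, the figures were 99.9% and 100%. The slope test gives practically the same answer whether or not LDL-C fell.

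**The case against.** The strongest reply concerns the reach of the D.1 sentence. It can be read as covering imaging endpoints only: enhancement is dichotomous and suits logistic regression, MFD is quantitative and suits linear regression, so lipids need not be outcomes. C.3 gives lipids a mechanistic role and pairs their change with imaging, and D.1 opens by pairing stenosis and PAV with lipids in the same way. This stands. A reader might infer that the plan certainly regresses lipid change on its own component; the text does not settle that. On the narrower reading, though, mean change in lipids has no stated analysis.

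A reader might also infer that such a lipid regression would always be strongly significant. That needs roughly equal SDs or a low r. At k = 0.75 and r = 0.5 the correlation is 0.28, p about 0.004 with 105 patients, and at r = 0.7 to 0.8 it is near zero. The coupling is direct only for LDL-C, HDL-C and lipoprotein(a), because apolipoprotein B and triglycerides are not D.1 predictors.

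Third, C.2 does not define enhancement or hemorrhage as a change, and the hypothesis in B.1 concerns stenosis and PAV. So the gap lies first in the endpoint definition, not in a defined change endpoint left without its test. A regression intercept could carry mean change if the outcome were a change and the predictors centred, but neither is stated.

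Fourth, a reader might take the lack of clustering in the secondary-endpoint sentence as an error. D.2 describes mixed effects for several arteries per patient, but in the PAV power paragraph. Whether enhancement and hemorrhage are analysed per artery or per patient is not stated, so this is an open question about the unit of analysis.

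**Conclusion.** The point holds in a limited form. No stated analysis estimates baseline-to-week-78 change in enhancement, hemorrhage, MFD or any lipid; this rests on the text alone. The self-regression problem is conditional on the D.1 sentence covering secondary endpoint 2. If it does, the built-in correlation for three of the five lipids is 0.71 to 0.32 for k = 1 and 0.60 to -0.08 for k = 0.75, over r from 0 to 0.8. All k and r values are assumptions, as are the enhancement rates in the illustration. Under any of them, the slope does not measure mean lipid change. The primary endpoints are not affected, because D.1 compares them with 0% change.

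**What to change.** In C.2, define enhancement, hemorrhage and MFD as changes from baseline to week 78, and state whether the unit is the artery or the patient. In D.1, analyse enhancement and hemorrhage with a mixed or GEE logistic model with a visit term, and MFD with a linear model with a visit term, clustered by patient where several arteries contribute. For each of the five lipids, report paired mean change with a 95% CI. Limit the on-treatment-lipid regressions to imaging outcomes and label them association analyses.

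The cost is SAP wording and a little more analysis; both scans and both lipid measurements are already scheduled. The added results have limits that the SAP should state. Without a control arm, paired changes are descriptive and cannot be attributed to the drug. Change in LDL-C is also open to regression to the mean, because B.3.a sets an LDL-C entry threshold, particularly if the qualifying value also serves as baseline.

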All drug compliance records will be kept current and will be made available for inspection by regulatory agency inspectors. Study drug will be given to patient at the baseline visit, and preferably at 6 month intervals thereafter. Instructions for shipping study drug to patients are provided in the appendix.

B.9. Study Timeline

There are two in-person study visits (baseline and 78 week follow-up) when patients will undergo vwMRI, approximately 60 minutes long, with a simultaneous clinical evaluation by a study investigator physician and blood draw. Every 2-4 months, the study coordinator will determine medication adherence, adverse events, or patient-reported recurrent stroke (see **Figure 1**).

	Screen/ Baseline	Day 1	Day 60	Day 120	Day 180	Day 240	Day 320	Day 480	Day 546
Informed Consent	Х								
Medical History/Current medications	х		х	х	х	Х	х	х	х
Vitals	Х								Х
Review CTA or MRA ¹	х								
Vessel wall MRI		Х							Х
Pregnancy test	Х								
Creatinine	Х								Х
Lipid panel	Х								Х
Lipoprotein (a)	Х								Х
Apolipoprotein B	Х								Х
Physical exam	Х								Х
Neurological exam	Х								х
NIHSS	Х								Х
Modified Rankin Scale	х								Х
Stroke adjudication			Х	Х	Х	Х	Х	Х	Х
Adverse event determination			х	Х	х	Х	х	х	х
Serious adverse events			Х	Х	Х	Х	Х	Х	Х

Figure 1: Schedule of Activities

1. To confirm ICAD of a major intracranial artery

B.10. Study Duration

- Estimated duration of research (study start to final study deliverable): 2 Years / 6 Months
- Estimated duration of first patient enrolled to last patient out: 2 Year / 0 Months
- Estimated duration for Amgen to supply study drug: 2 Year / 0 Months

C. Study Endpoints

C.1. Primary Endpoints

The primary endpoints are nominal change in the stenosis and percent atheroma volume (PAV) of cerebrovasculture arteries from baseline to week 78. We will use measure stenosis and PAV on vessel wall MRI (vwMRI), which evaluates all arteries from the aortic arch to the distal intracranial vasculature in a single scan. The primary endpoints will be analyzed for both: 1) all intra- or extracranial arteries that have at least 25% stenosis, and 2) seperately for the intracranial arteries. Stenosis and PAV will be measured using standard methodology.

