We power our study on the primary endpoint of change in stenosis and PAV. The GLAGOV trial showed 0.95% reduction in PAV for patients randomized to Repatha versus a 0.05% increase in PAV for patients in the placebo arm and was 78 weeks in length. Because the major intracranial arteries have a similar luminal diameter to coronary arteries, we may reasonably expect a 1% reduction in PAV for our 78 week study as documented in previous literature. Patients with intracranial atherosclerosis can be expected to have at least 3 additional sites of atherosclerosis, including extracranial arteries, that will be included in the series of PAV outcomes. Each subject will provide four sites of atherosclerosis and therefore, 4 PAV measurements. This cluster designed study will be modeled by a mixed effects linear regression to account for the cluster of arteries per patient. We obtain >80% power for our sample size of 150 patients, two-sided significance level 0.05, and a conservative assumed standard deviation of 4% from previous studies for the assumed 1% reduction in PAV against the documented control PAV of 0%.²³ With 150 patients, the minimum effect size possible to detect with 80% power is a 0.51% reduction. A 0.50% difference has been reported to be the cutoff to distinguish individuals that experience cardiovascular events versus those who do not.²³ Assuming a withdrawal rate of 25-30%, we would still reach >90% power for a 1% reduction with the above-listed conditions. We do not expect to show a significant reduction in recurrent stroke, but anticipate seeing a trend towards that outcome. This data could be used to accurately construct and power a subsequent trial with the primary outcome of recurrent stroke. Finally, in GLAGOV the linear relationship between change in stenosis, PAV and on-treatment LDL-C was very robust. We will be replicate this finding through means of a generalized linear mixed effects model. Our effective sample size may be sufficiently large enough to match the GLAGOV trial as each patient will be able to contribute an average of 4 arteries giving us an expected sample size between 800 and 1200 dependent on a conservative prediction of intra-class correlation. All reported p-values will be twosided and deemed significant at the 0.05 level.

D.3. Loss to Follow-up

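### Between 9 and 44 lipid-by-imaging association tests each face the 0.05 threshold of D.2 with no adjustment, testing order or exploratory label

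*Combined protocol and SAP*

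**What the plan says.** Three sections of the protocol bear on this.

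- **C.3 (Secondary endpoint 2)** gives its purpose as "To better understand the mechanism of Repatha's effect on intra- and extracranial atherosclerosis". It lists five markers, "change in cholesterol markers [LDL-C, HDL-C, lipoprotein (a), apolipoprotein B, and triglyceride level", and adds: "The change in cholesterol markers will be correlated with the primary and secondary study endpoints on vwMRI". Recurrent stroke, introduced in the same section, is the only outcome called exploratory.
- **D.1 (Statistical methods)** plans logistic or linear regression for the secondary endpoints and will "use the primary predictors of on-treatment LDL-C, HDL-C, and lipoprotein(a"). The three lipids are listed side by side.
- **D.2 (Power Analysis)** ends with the rule "All reported p-values will be twosided and deemed significant at the 0.05 level".

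The imaging outcomes are set in C.1 and C.2. On the primary side, "The primary endpoints are nominal change in the stenosis and percent atheroma volume (PAV"), analysed for "all intra- or extracranial arteries that have at least 25% stenosis, and 2) seperately for the intracranial arteries". On the secondary side, "Secondary endpoint 1 is post-contrast plaque enhancement for intracranial arteries and intraplaque hemorrhage for the cartotid artery". MRA flow dynamics is a third measure, listed under C.2.a but not named in the opening definition of C.2.

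The protocol contains no multiplicity adjustment, gatekeeping or testing order, and it does not count these tests.

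**The concern.** The lipid-by-imaging analyses are meant to explain how the drug acts. The study has one arm, and its primary endpoints are compared with an assumed 0% change, so these associations are an important part of the internal evidence linking lipid lowering to plaque change. A.5 says that the data will be used to design a later trial.

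A flat 0.05 rule over a large, uncounted set of tests does not hold the chance of a spurious finding at 5%. D.2 gives a prior basis for one relation only: on-treatment LDL-C with stenosis and percent atheroma volume. Under the D.2 rule, a chance association of another lipid with another imaging measure would carry the same significance wording. It could then influence the choice of biomarkers for the next trial.

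**Working it through.** **The plan's own figure.** The only figure is 0.05, two-sided, for each reported p-value. No family-wise rate is stated, so there is none to reproduce.

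**Step 1: count the tests.** Inputs:

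- Lipid changes in C.3: 5.
- On-treatment lipids in D.1: 3.
- Primary imaging outcomes in C.1: 2 (stenosis, percent atheroma volume), or 4 if both artery sets count.
- Secondary imaging outcomes in C.2 and C.2.a: 3 (plaque enhancement, carotid intraplaque hemorrhage, flow dynamics), or 2 without flow dynamics.

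Readings:

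- D.1 secondary-endpoint regressions only: 3 × 3 = 9.
- C.3 and D.1 as one analysis with three predictors: 3 × (2 + 3) = 15.
- C.3 only: 5 × (2 + 3) = 25.
- C.3 and D.1 separate, without flow dynamics: 5 × (2 + 2) + 3 × 2 = 26.
- C.3 and D.1 separate: 25 + 9 = 34.
- The same with both artery sets: 5 × (4 + 3) + 9 = 44.

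None of these counts, except the 15, includes the separate D.1 models of stenosis and percent atheroma volume on the three on-treatment lipids.

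**Step 2: chance of at least one false positive.** Take all k associations as null.

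- Independent tests: 1 − 0.95^k. For k = 9 this is 1 − 0.95^9 = 0.370. For k = 34 it is 1 − 0.95^34 = 0.825.
- Equal correlation ρ between test statistics: 1 − ∫ [Φ((1.96 − √ρ·u)/√(1−ρ)) − Φ((−1.96 − √ρ·u)/√(1−ρ))]^k φ(u) du, integrated numerically.

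The documents give no correlations, so ρ is an assumption and is shown as a range.

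| k | ρ = 0 | ρ = 0.5 | ρ = 0.8 |
|---|---|---|---|
| 9 | 37.0% | 26.9% | 16.5% |
| 15 | 53.7% | 36.1% | 20.2% |
| 25 | 72.3% | 46.7% | 24.2% |
| 26 | 73.6% | 47.5% | 24.5% |
| 34 | 82.5% | 53.5% | 26.6% |
| 44 | 89.5% | 59.3% | 28.8% |

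The smallest entry is 16.5%, and 16.5/5 = 3.3. The expected number of false positives is 0.05k whatever the correlation: 0.45 for 9 tests, 1.7 for 34 and 2.2 for 44.

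**Step 3: a less uniform correlation pattern.** Simulation of the 34 tests with 105 or 150 patients used assumed correlations by pair.

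- Moderate (LDL-C with apolipoprotein B 0.8, stenosis with atheroma volume 0.5, change with on-treatment value 0.7): about 75%.
- High (0.9, 0.8 and 0.9 for the same pairs): about 65%.
- All lipids and all imaging outcomes correlated at 0.7: 43-50%, and lower above that.

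**Step 4: drop the tests most likely to be real.** Ten of the 34 (5 lipid changes × 2) concern stenosis and percent atheroma volume. Without them 24 remain. The chance is 70.8% if independent, 45.8% at ρ = 0.5, and 54-63% under the two patterned simulations.

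**The case against.** The strongest case on the other side has four parts.

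**A reader might infer that a false mechanism finding is more likely than not.** The documents do not support that. It requires every tested association to be null, while D.2 expects at least the on-treatment LDL-C relation with stenosis and atheroma volume to be real. It also depends on the count and on the correlation. Independent tests pass 50% only from 14 upward (13 give 48.7%, 14 give 51.2%). The D.1 secondary-endpoint regressions reach 37% at most, and the range for 34 straddles one half. This part of the objection stands.

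**Thirty-four is a construction.** C.3 may state the aim and D.1 the method for a single analysis, and the protocol does not say. C.3 also does not promise a p-value for each correlation, and D.2 governs reported p-values only. This stands as a reason to give a range. Against it, the two sections differ in lipid quantity (change against on-treatment value), lipid list and outcome set, so reading them as separate is reasonable.

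**The lipids are partly ranked.** D.1 leaves triglycerides and apolipoprotein B out of its primary predictors, and D.2 singles out LDL-C. Endpoints are also sorted into primary, secondary and exploratory tiers. So it would be wrong to say that the plan has no hierarchy. What is missing is a testing order, or an exploratory label, for these associations.

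**Control of secondary mechanistic tests is a convention.** In a single-arm study meant to inform a later trial, no decision rule hangs on these tests, so the consequence is modest. That limits the weight of the point. It does not remove it, because D.2 applies the significance label explicitly and without limit.

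**Conclusion.** The point holds in a limited form. The plan declares significance at 0.05 for an uncounted set of lipid-by-imaging tests, without adjustment, order or exploratory label. If the tested associations are null, the chance of at least one false positive is about 17-37% on the narrow reading of 9 tests and 27-83% for 34. That is at least three times 5% on every reading tabulated. It rests on three assumptions: the null condition, the reading of C.3 and D.1 that sets the count, and a correlation between tests of 0 to 0.8 that the documents do not supply.

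A reader might go further and conclude that LDL-C should be the only lipid tested for significance on the secondary imaging endpoints, in a particular order. The documents do not support that either. D.1 names HDL-C and lipoprotein(a) as primary predictors too, and nothing ranks enhancement, hemorrhage and flow. This is a worthwhile and inexpensive correction to secondary analyses. It does not bear on whether the primary comparison is valid.

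**What to change.** 1. In C.3 and D.1, say whether the change correlations and the on-treatment regressions are one analysis or two, and label the lipid associations with the vessel wall MRI endpoints exploratory. The exception is the on-treatment LDL-C relation with stenosis and percent atheroma volume that D.2 sets out to replicate.
2. Report the exploratory associations as estimates with 95% confidence intervals and no significance wording.
3. Limit the last sentence of D.2 to the primary endpoints and that LDL-C relation.
4. If the sponsor wants a significance claim on any secondary imaging endpoint, it should choose and write down its own testing order or adjustment before the imaging reads. C.1.a places the reads at the completion of enrollment. For scale, a Bonferroni level would be 0.05/9 = 0.0056 for 9 tests and 0.05/34 = 0.0015 for 34.

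The cost is wording in three sections. No new data are needed and no planned estimate is lost. The small downside is that the remaining associations become hypothesis-generating only. The change does not address multiplicity among the primary endpoints themselves, which is a separate question.

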B.6. Patient Withdrawal

A patient has the right to withdraw from the study at any time, for any reason, and without repercussion. The investigator has the right to withdraw a patient from the study in the event of an intercurrent illness, adverse event, treatment failure, protocol violation, cure, and for administrative or other reasons. An excessive rate of withdrawals would render the study uninterpretable; therefore, unnecessary withdrawal of patients will be avoided. Should a patient (or a patient's legally authorized guardian or representative) decide to withdraw, all efforts will be made to complete and report observations as thoroughly as possible. Early termination procedures will be followed.

B.7. Patient Replacement

Patients prematurely withdrawn from the study can be replaced, if needed, to ensure an adequate number of evaluable patients. The investigator, (in cooperation with the study statistician, if applicable) will decide whether or not to replace withdrawn patients.

B.8. Investigation Drug Management

At each study site, the drug management will be performed by their respective Investigational Drug Services (IDS). Study drug will be refrigerated at the site at a temperature of 2 to 8°C; refrigerator temperature will be logged daily. At no time, will product be left unattended or outside the control of an individual knowledgeable with regard to product temperature requirements. Moreover, no one will administer product that has not been maintained according to temperature requirements. Study drug will be shipped at a temperature of 2 to 8°C to the investigator or designee at regular intervals or as needed during the study. During site close-out, and following drug reconciliation and documentation, all opened and unopened vials of study drug will be kept current. The primary investigator will account for all opened and unopened vials of study drug. These records will contain the dates, quantity, and study medication:

- a) dispensed to each patient,
- b) returned from each patient (if applicable), and
- c) disposed of at the site or returned to Amgen Inc. or designee

All accountability records will be made available for inspection by regulatory agency inspectors.

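### Recurrent stroke appears set to be regressed on on-treatment lipids first measured at week 78, after or at the same visit as the events, so the slope can reflect what a stroke did to lipids

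*Combined protocol and SAP*

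**What the plan says.** D.1 (Statistical methods) sets logistic and linear regression for the secondary endpoints and says these will "use the primary predictors of on-treatment LDL-C, HDL-C, and lipoprotein(a"). The next sentence turns to stroke: "For the exploratory endpoint of recurrent stroke, we will use the above mentioned methods as well as a Cox proportional hazards model". The Cox part continues "with the observed rate in this study compared to controls matched according to degree to stenosis of the index artery".

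On lipid timing, C.3 states: "Cholesterol values will be measured at the baseline and comparison MRIs, which are 78 weeks apart". The schedule of activities (Figure 1, B.9) agrees: the lipid panel and lipoprotein(a) are marked at Screen/Baseline and Day 546 only. The one alternative source is routine care, limited by C.3 to a window around a visit: "If standard of care lab values are available within 30 days of the study visit".

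On stroke timing, C.3 defines the composite as "new patient-reported symptomatic ischemic stroke, transient ischemic attack, or asymptomatic strokes that emerge between MRIs". Figure 1 marks stroke adjudication at Days 60, 120, 180, 240, 320, 480 and 546. Between visits, B.9 provides contact without a blood draw: "Every 2-4 months, the study coordinator will determine medication adherence, adverse events, or patient-reported recurrent stroke".

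On what may change after an event, B.6 says: "The investigator has the right to withdraw a patient from the study in the event of an intercurrent illness, adverse event, treatment failure". Nothing in the plan holds background lipid therapy fixed after a stroke.

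**The concern.** A regression of stroke on on-treatment LDL-C is normally read as asking whether lower LDL-C on treatment goes with fewer strokes. That reading needs the lipid value to come before the event. Here each patient has one on-treatment value, taken at the end. If a stroke or TIA leads to a change in background lipid therapy, in adherence or in whether injections continue, the Day 546 value is partly a result of the event.

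The bias has no fixed sign. If LDL-C falls after events, low LDL-C will seem to accompany stroke. If patients stop injecting after events, high LDL-C will. Either can occur when lipids and stroke are unrelated. D.2 calls any two-sided p below 0.05 significant, and D.1 has no landmark, time-updated or pre-event rule that would prevent this. The risk is that a published lipid-stroke slope is taken as evidence of mechanism when it may reflect care after the stroke.

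**Working it through.** The documents give no event rate, effect size or power for this regression, so there is no planned figure to reproduce. The check has two parts.

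**1. Time order (from the documents).**

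| Quantity | When measured |
|---|---|
| Baseline lipids | Screen/Baseline |
| Symptomatic stroke, TIA | Any time between the MRIs, adjudicated Day 60 to Day 546 |
| Silent infarct | Seen on the second MRI, Day 546 |
| On-treatment lipids | Day 546, or routine care within 30 days of a visit |

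Symptomatic events therefore generally precede the on-treatment lipid value, and silent infarcts are detected at the same visit. The schedule has no on-treatment draw that comes before the events.

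**2. Possible size (conditional on assumptions).**

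From the documents: 150 patients (B.2), up to 30% without the final visit (D.3), two-sided 0.05 (D.2). Completers: 150 × 0.70 = 105.

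Assumed, because the documents are silent: event risk 10-15% among completers, so 105 × 0.10 = 10.5 to 105 × 0.15 = 15.75 events; Day 546 LDL-C mean 40 and SD 25 mg/dL; no true relation; a stated shift in LDL-C in a stated share of event patients.

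Closed-form check for a shift Δ in every event patient. With normal LDL-C of equal SD in both groups, the logistic slope is Δ/SD² per mg/dL.
- Δ = −10: 10 × (−10/625) = −0.16, OR = exp(−0.16) = 0.85 per 10 mg/dL.
- Δ = −20: 10 × (−20/625) = −0.32, OR = exp(−0.32) = 0.73.

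The standard error of the mean difference is 25 × √(1/10.5 + 1/94.5) = 8.13 at 10% risk and 25 × √(1/15.75 + 1/89.25) = 6.83 at 15%.
- Δ = −10: z = 10/8.13 = 1.23 and 10/6.83 = 1.46, so rejection is about 23% and 31%.
- Δ = −20: z = 2.46 and 2.93, so about 69% and 83%.

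Simulated logistic regressions (stroke drawn independently of LDL-C, the shift applied afterwards, Wald test) give slightly lower rates, as expected with few events. The ranges below cover both event risks and several independent runs, some with normal and some with skewed LDL-C.

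| Change in Day 546 LDL-C after an event | Rejection at 0.05 | Direction of slope |
|---|---|---|
| None | about 4-5% | none |
| 10 mg/dL lower in a quarter to half, 20 lower in a quarter, or 45 higher in a tenth | about 4-11% | either |
| 10 lower in all, or 20 lower in half | about 16-29% | low LDL-C with stroke |
| 45 higher in 30% | about 33-48% | high LDL-C with stroke |
| 20 lower in all (extreme) | about 55-80% | low LDL-C with stroke |

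A second simulation asked what happens when there is a true effect: 110 completers, LDL-C mean 40 and SD 20 mg/dL, true OR 1.10 per 10 mg/dL, event risk 10-20%. The median estimated OR is 0.94-0.95 if half of stroke patients have LDL-C cut by 25%, 0.80 if all do, and 1.38-1.40 if a quarter stop the drug (+50 mg/dL). With LDL-C taken before the event it is 1.09-1.11, but power is only 9-11% and the sign is wrong by chance in 24-29% of runs.

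**The case against.** Five points can be made for the plan.

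- **The link is by reference.** D.1 names the lipid predictors for the secondary endpoints and reaches recurrent stroke only through a general phrase. This stands as a caution: the lipid regression is the natural reading, not an explicit statement. The same phrase might import the adjustment for statin use and dose that D.1 names for the primary endpoints. The plan does not say when the dose is recorded, and a dose recorded at week 78 could itself follow from the event, so this is not a clear cure.
- **The Cox model.** A reader might infer that it also carries Day 546 lipids as a fixed covariate. D.1 does not support that. It describes a comparison of the observed rate with stenosis-matched controls and names no lipid term.
- **Silent infarcts.** Those found only on the second scan would not ordinarily have changed therapy before the lipid draw. This stands and dilutes the bias, so shifts in every event patient are upper cases.
- **Withdrawn patients.** Event patients who leave under B.6 may have no Day 546 value and would drop out of the regression. That limits this mechanism but raises a separate selection question.
- **Weight.** The endpoint is exploratory, and D.2 expects no significant stroke reduction. A reader might infer that the lipid slope will size the next trial. D.2's remark about future use follows sentences on the stroke reduction and its trend, and says nothing about a lipid slope.

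**Conclusion.** The point holds for the logistic or linear regression of recurrent stroke on on-treatment lipids. The predictor is measured after the outcome or at the same visit, and the plan has nothing to prevent a stroke from influencing it. The Cox comparison with matched controls is outside the point.

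The size cannot be fixed from the documents. Under the stated assumptions, the false-positive rate runs from near nominal (about 4-11%) for small reactions, through 16-29% for moderate ones and 33-48% in the opposite direction when 30% of event patients have LDL-C 45 mg/dL higher, to about 55-80% in the extreme case. A reader might conclude that the slope will point the wrong way or that the extreme figure is typical. Neither follows: the direction depends on what happens after a stroke, which the plan does not describe, and silent infarcts pull the result toward nominal.

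Severity is low. The endpoint is exploratory, and with about 10-16 events under these assumptions the regression would be imprecise even with correctly timed lipids.

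**What to change.** Change the wording of D.1 only:

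- State that Day 546 lipids will not be used as predictors of recurrent stroke.
- Use the baseline LDL-C, HDL-C and lipoprotein(a) already collected at Screen/Baseline if a lipid-stroke regression is kept.
- Report the recurrent stroke rate with an exact confidence interval.
- Show Day 546 lipids by stroke status as description, without a p-value.
- Leave the Cox comparison with matched controls as it is on this point.

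No new visit or sample is needed. Entering an on-treatment lipid value dated before the event is not an option under the current schedule, which has no such draw. The cost is that no on-treatment lipid-stroke slope is reported. The baseline regression answers a different question, and with few events it will be imprecise, so it should be presented as an estimate with its interval.
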